## 4. EFFICACY

Efficacy data will be summarized for the ITT Analysis Sets (full and enriched) and listings will be created for the All Subjects Set.

The efficacy variables in this study are listed in Table 2.

**Table 2: Efficacy Variables**

Endpoint	Scale*	
Primary	HDRS 17 total score	
	HDRS 17 ≥30% improvement from double-blind treatment baseline on total score	
	HDRS 17 ≥50% improvement from double-blind treatment baseline on total score (clinical response)	
	HDRS 17 clinical remission	
	HDRS 17 anxiety/somatization factor score	
	Secondary	HAM-D 6 score
		SIGH-A total score
		SIGH-A ≥30% improvement from double-blind treatment baseline on total score
		SIGH-A ≥50% improvement from double-blind treatment baseline on total score
		HAM-A 6 score
Patient Reported Outcomes	CGI-I	
	Clinically Useful Depression Outcome Scale (CUDOS-A)	
	Cognitive and Physical Functioning Questionnaire (CPFQ)	
	Snaith-Hamilton Pleasure Scale (SHAPS)	
	Medical Outcomes Study Sleep-Revised (MOS Sleep-R)	
Patient Reported Outcomes	Perceived Stress Scale (PSS)	
	Self-Assessment of Treatment Experience (SATE)	

\* HDRS17 Hamilton Depression Rating Scale; HAM D6 Hamilton Depression Rating Scale; SIGH A Structured Interview Guide for the Hamilton Anxiety Scale; HAM A6 Hamilton Anxiety Rating Scale ; CGI I Clinical Global Impression – Improvement.

### 4.1. Analysis Specifications

#### 4.1.1. Level of Significance

The overall type I error rate for testing the JNJ-42165279 group versus the placebo group for the primary efficacy analysis will be controlled at the 1-sided significance level of 0.20.

#### 4.1.2. Imputation Methods for Missing Items

Imputation of missing individual items will apply only to the HDRS17, as described in Section 4.2.1. For all other scales where multiple items are summed to create a total score, if any item of the scale is missing on a visit, the total score for that scale at that visit will be left blank.

### 4.2. Primary Efficacy Endpoint – HDRS17 Total Score

The primary efficacy endpoint is the change from Baseline in HDRS17 total score at Week 6 of the double-blind treatment period.

### 4.2.1. Definition

The HDRS17 is a clinician-administered rating scale designed to assess the severity of symptoms in subjects diagnosed with depression (Hamilton M 1960). It is the most widely used symptom severity measure for depression. Each of the 17 items is rated by the clinician on either a 3- or a 5-point scale. Higher scores indicate greater severity of depression. The HDRS17 total score will be calculated as the sum of the 17 item scores, and ranges from 0 to 52. If one HDRS17 Total Score item is missing, it will be imputed with the closest integer to the average of the remaining items at that time point. If more than 1 item is missing, no imputation will be performed and the HDRS17 Total Score will be missing. Imputation of item scores is performed prior to determining the endpoint for the HDRS17 Total Score.

### 4.2.2. Estimand

The primary estimand, the main clinical quantity of interest to be estimated in the study, is defined by the following 4 components:

- **Population:** Subjects with a primary DSM-5 diagnosis of MDD with Anxious Distress
- **Variable:** Change from baseline to Week 6 of the double-blind treatment period in HDRS17 total score
- **Intercurrent event:** No intercurrent events to be taken into account
- **Population-level summary:** Difference in mean change from baseline to Week 6 of the double-blind treatment period in HDRS17 total score between treatment conditions.

### 4.2.3. Analysis Methods

#### 4.2.3.1. Primary Analysis

The primary efficacy analysis will be based on the eITT set.

Descriptive statistics of actual values and mean changes from baseline for the HDRS17 total score at each scheduled time point will be provided by treatment group for the lead-in period, the double-blind treatment period and the withdrawal period for the eITT set. A mean-SE plot over time will be presented for the HDRS17 total score observed values during the lead-in period, the double-blind treatment period and the withdrawal period by treatment group. Listings will be created with HDRS17 item scores and the HDRS17 total score.

The JNJ-42165279 treatment group will be compared with placebo using the change from double-blind treatment baseline in the HDRS17 total score during the double-blind treatment period. The comparison will be performed with a mixed-effects model using repeated measures (MMRM), with time, treatment (placebo, JNJ-42165279) and time-by-treatment interaction as factors, double-blind treatment baseline total HDRS17 score as a continuous covariate, and country as categorical covariates. An unstructured variance-covariance matrix will be used. In case of convergence problems, simpler variance-covariance structures such as Toeplitz or AR(1) will be considered. The selection of any of these structures will be determined after exploration of the

observed correlation structure. The treatment-placebo differences will be obtained using the appropriate contrast in the MMRM models at the 6-week endpoint. A one-sided p-value with level of significance of 20% will be derived from the SAS results based on the above mixed-effects model (two-sided p-values at 40% significance level). The reduction in HDRS17 total score is expected to be larger after dosing with JNJ42165279, so the one-sided p-value will be calculated as described in the table below.

#### **Calculation of one-sided p-value**

Parameter	Ha	Estimated difference MeanJNJ – MeanPla	One-sided p-value
Change in HDRS 17 total score at Week 6	Mean Chg JNJ - Mean Chg Pla < 0 (larger reduction expected in JNJ vs pla)	≤ 0	p-value (2-sided test) / 2
		> 0	1 – (p-value (2-sided test) / 2)

Least-square mean changes from baseline (+/-SE) over time during the double-blind treatment period will be presented in a figure.

#### **4.2.3.2. Additional Analysis**

To assess the sensitivity of the results of the MMRM analysis of the primary endpoint, an analysis of covariance (ANCOVA) model for the change from baseline to the 6-week double-blind treatment endpoint in HDRS17 total score will be carried out. The ANCOVA model will include factors for treatment and (pooled) center and double-blind treatment baseline HDRS17 total score as a covariate. In addition, the same ANCOVA model will also be performed on observed case data at week 6 of the double-blind treatment period.

As a secondary analysis, the MMRM model described in Section 4.2.3.1 will be fitted with age, sex and duration of antidepressant treatment (in days) as additional covariates.

The primary analysis specified in Section 4.2.3.1. will also be performed for the fITT set. Treatment effect for the fITT set will be estimated in 2 manners: using the same MMRM model as for the primary analysis and using the MMRM model with lead-in response status as additional categorical covariate.

To explore the results for the subgroup of placebo responders, descriptive statistics of actual values and mean changes from baseline for the HDRS17 total score at each scheduled time point will be provided by treatment group for the lead-in period, the double-blind treatment period and the withdrawal period for the fITT subset of placebo responders. A mean-SE plot over time will also be presented for this subgroup.

### **4.3. Secondary Efficacy Endpoints**

#### **4.3.1. Definition**

The following secondary efficacy variables are used to measure depressive symptoms in subjects:

- **HDRS17 ≥30% improvement from double-blind treatment baseline on total score:** the percentage change from double-blind treatment baseline is calculated as

$$100 * \frac{(HDRS_{17} \text{ total score at any time point} - HDRS_{17} \text{ total score at baseline})}{HDRS_{17} \text{ total score at baseline}}$$

A ≥30% improvement from double-blind treatment baseline on total score means that the percentage from baseline is ≤ -30 in this calculation.

- **HDRS17 ≥50% improvement from double-blind treatment baseline on total score (clinical response):** the percentage change from double-blind treatment baseline is calculated in the same way as for the ≥30% definition. A ≥50% improvement from double-blind treatment baseline on total score means that the percentage from baseline is ≤ -50 in this calculation.
- **HDRS17 clinical remission:** Clinical remission is defined as having a HDRS17 total score ≤ 7.
- **HDRS17 anxiety/somatization factor score:** The HDRS17 anxiety/somatization factor derived from Cleary and Guy's factor analysis of the HDRS17 scale, includes six items from the original 17-item version: the items for psychic anxiety, somatic anxiety, gastrointestinal somatic symptoms, general somatic symptoms, hypochondriasis, and insight. The HDRS17 anxiety/somatization factor score will be calculated as the sum of the 6 item scores, and ranges from 0 to 18, with higher scores indicating greater severity of symptoms.
- **HAM-D6 subscale score:** A 6-item subscale from the HDRS17 (HAM-D6) will be analyzed as it has been shown to be a uni-dimensional scale that provides information to core depressive symptoms and is sensitive to treatment response (Bech 1975). The six items are: depressed mood, guilt feelings, work and interests, psychomotor retardation, psychic anxiety, and general somatics (tiredness and pains). The HAM-D6 score will be calculated by summing the 6 items scores, and ranges from 0 to 22. Higher scores indicate greater severity of core symptoms.
- **Structured Interview Guide for the Hamilton Anxiety scale (SIGH-A):** The original HAM-A scale assesses the severity of different anxiety-related symptoms (Hamilton 1959; Hamilton 1969). It is the most widely used symptom severity measure for anxiety. As the original HAM-A scale lacks instructions for administration and clear anchor points for the assignment of severity ratings, the structured interview guide version (SIGH-A) is used in the current study. The SIGH-A has been shown to have high inter-rater and test-retest reliability and produced similar but consistently higher (+ 4.2) scores compared to the original HAM-A. The SIGH-A scale consists of 14 items with a score of 0 to 4. Higher scores indicate higher severity (0-absent, 1-mild, 2-moderate, 3-severe, 4-incapacitating). The SIGH-A total score will be calculated by summing the 14 item scores, and ranges from 0 to 56. Higher scores indicate worse results.

- **SIGH-A  $\geq 30\%$  improvement from double-blind treatment baseline on total score:** the percentage change from double-blind treatment baseline is calculated as

$$100 * \frac{(\text{SIGH} - A \text{ total score at any time point} - \text{SIGH} - A \text{ total score at baseline})}{\text{SIGH} - A \text{ total score at baseline}}$$

A  $\geq 30\%$  improvement from double-blind treatment baseline on total score means that the percentage from baseline is  $\leq -30$  in this calculation.

- **SIGH-A  $\geq 50\%$  improvement from double-blind treatment baseline on total score:** the percentage change from double-blind treatment baseline is calculated in the same way as for the  $\geq 30\%$  definition. A  $\geq 50\%$  improvement from double-blind treatment baseline on total score means that the percentage from baseline is  $\leq -50$  in this calculation.
- **HAM-A6 subscale score:** The HAM-A6 is a 6-item subscale derived from the original Hamilton Anxiety scale (HAM-A). It comprises five psychic anxiety symptoms: anxious mood, psychic tension, fears, intellectual disturbances, and anxious behavior observed at the interview, as well as one somatic item, muscular tension. The HAM-A6 score will be calculated by summing the 6 item scores, and ranges from 0 to 24. Higher scores indicate greater severity of symptoms.
- **Clinical Global Impression Improvement (CGI-I):** The CGI-I is a 7-point scale that requires the clinician to assess how much the subject's illness has improved or worsened relative to a baseline state at the beginning of the intervention. The CGI-I is rated as: 1 very much improved; 2 much improved; 3 minimally improved; 4 no change; 5 minimally worse; 6 much worse; 7 very much worse. Responders on the CGI-I are defined as subjects with a score of 1 very much improved or 2 much improved.

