For inclusion, subjects must have a HDRS₁₇ total score ≥ 18 and a HDRS₁₇ anxiety/somatization factor score ≥ 7 while having been treated with one of the antidepressants approved in this protocol at an adequate dose and for at least 6 continuous weeks. The clinical history of the current episode of MDD will be assessed by the MINI and supplementary subject validation questions; the lack of response to antidepressant therapy symptom severity will be assessed by the HDRS₁₇, and the antidepressant treatment history based on the subject's report during the screening interview by the ATRQ. Each of these assessments will be conducted by qualified personnel at the site at screening and will be recorded to allow independent validation of the suitability of the subject for enrollment by an independent central rater contracted by the sponsor.

Screening will include obtaining informed consent, assessment of study inclusion and exclusion criteria, medical history, physical examination, neurological examination and safety evaluations.

The screening visit may be split into 2 visits.

Adverse events will be collected starting after the informed consent form (ICF) has been signed until the final study procedure at the final visit.

Subjects who are deemed eligible for randomization will enter the double blind treatment phase.

Double Blind Treatment Phase

Subjects who successfully complete the screening will visit the clinical site/unit on Day 1.

Lead-in period

Subjects who successfully complete the screening will visit the clinical site/unit on Day 1 and will be treated with placebo for the entire duration of the lead-in period. Investigators and subjects will be blinded to exact duration of each subject-specific lead-in period throughout the study.

Treatment period

At the end of the lead-in period both: placebo lead-in responders and placebo lead-in non-responders will be randomized to receive either adjunctive placebo or JNJ-42165279 in a 1:1 ratio for a 6 week in treatment period.

Investigators and subjects will remain blinded to exact timing of the randomization and study drug treatment assignment for each subject.

Withdrawal period

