Attachment 2: Clinical Global Impression – Improvement (CGI-I)

Rate total improvement whether or not, in your judgment, it is due entirely to drug treatment. Compared to his/her condition at admission to the project, how much has the patient changed?

- 0 = Not assessed
- 1 = Very much improved
- 2 = Much improved
- 3 = Minimally improved
- 4 = No change
- 5 = Minimally worse
- 6 = Much worse
- 7 = Very much worse

Reproduced from Guy W, editor. ECDEU Assessment Manual for Psychopharmacology. 1976. Rockville, MD, U.S. Department of Health, Education, and Welfare

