## 1.2. Trial Design

This is a multi-center, double-blind, placebo-controlled, randomized, parallel-group study in subjects with MDD with anxious distress who have had inadequate response to SSRI/SNRI treatment.

Subjects who meet the inclusion and exclusion criteria and are enrolled will be maintained on the SSRI/SNRI treatment throughout the study to determine whether adjunctive treatment with JNJ-42165279 can reduce symptoms of MDD with anxious distress.

[figure not shown]
For each subject, the study will consist of three phases: a screening phase of up to 4 weeks, a treatment phase lasting up to 11 weeks, and a 3-week post-treatment (follow up) phase. The treatment phase of the trial will consist of 3 periods. The first period is a placebo lead-in of 3 weeks for all subjects, after which subjects will enter the double-blind treatment period when they will be randomly assigned to JNJ-42165279 or continuation on placebo for 6 weeks. Subjects who successfully complete the double-blind treatment period will be treated with placebo during a 2-week withdrawal period. The total study duration for each subject will be approximately 18 weeks.

The end of study is defined as the date of the last visit of the last subject undergoing the trial. Investigators and subjects will remain blinded to the exact duration of the subject lead-in and withdrawal period during the entire study duration.

Approximately 143 subjects will enter the double-blind placebo lead-in period. At the end of the lead-in period, response status of the subjects will be assessed according to the double-blind response criteria based on reduction in HDRS17 relative to lead-in baseline. Both lead-in placebo responders and lead-in placebo non-responders will be randomly assigned in a 1:1 ratio to either 25 mg of JNJ-42165279 or placebo in the treatment period. The primary efficacy analyses will be based on the treatment period data from the lead-in non-responders (94 subjects).

An overall flow diagram of the study is shown in the figure below.

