	4	Lead-in Week 2	11 to 17	14	Lead-in
	5	Lead-in Week 3	18 to 24	21	Lead-in
	5	DB Treatment Baseline	<=1	1	DB Treatment
	6	DB Treatment Week 1	2 to 10	7	DB Treatment
	7	DB Treatment Week 2	11 to 21	14	DB Treatment

Parameter	Scheduled Visit Number	Time Interval (label on output)	Time Interval (Day) 	Target Time Point (Day) by Period	Analysis Phase
	8	DB Treatment Week 4	22 to 35	28	DB Treatment
	9	DB Treatment Week 6	36 to 49	42	DB Treatment
	9	DB Treatment End Point 			DB Treatment
	9	Withdrawal Baseline	<=1	1	Withdrawal
	10	Withdrawal Week 2	2 to 20	14	Withdrawal
CGI-I	3	Lead-in Week 1	2 to 10	7	Lead-in
	4	Lead-in Week 2	11 to 17	14	Lead-in
	5	Lead-in Week 3	18 to 24	21	Lead-in
	5	DB Treatment Baseline	<=1	1	DB Treatment
	6	DB Treatment Week 1	2 to 10	7	DB Treatment
	7	DB Treatment Week 2	11 to 21	14	DB Treatment
	8	DB Treatment Week 4	22 to 35	28	DB Treatment
	9	DB Treatment Week 6	36 to 49	42	DB Treatment
	9	DB Treatment End Point 			DB Treatment
	9	Withdrawal Baseline	<=1	1	Withdrawal
	10	Withdrawal Week 2	2 to 20	14	Withdrawal
Physical Examination	1	Screening	< 1	-28 to -1	Screening
	10	Withdrawal Week 2	2 to 20	14	Withdrawal
	11	Follow Up	> DB or >Withdrawal	7 to 21	Follow Up
Neurological Examination	1	Screening	< 1	-28 to -1	Screening
	7	DB Treatment Week 2	2 to 21	14	DB Treatment
	9	DB Treatment Week 6	22 to 49	42	DB Treatment
	10	Withdrawal Week 2	2 to 20	14	Withdrawal
Vital Signs, Body Temperature, Body Weight, Clinical Laboratory Assessments, 12-lead ECG	1	Screening	<1	-28 to -1	Screening
	2	Lead-in Baseline	<=1	1	Lead-in
	3	Lead-in Week 1	2 to 14	7	Lead-in
	5	Lead-in Week 3	15 to 28	21	Lead-in
	5	DB Treatment Baseline	<=1	1	DB Treatment
	7	DB Treatment Week 2	2 to 21	14	DB Treatment
	8	DB Treatment Week 4	22 to 35	28	DB Treatment
	9	DB Treatment Week 6	36 to 49	42	DB Treatment

Parameter	Scheduled Visit Number	Time Interval (label on output)	Time Interval (Day) 	Target Time Point (Day) by Period	Analysis Phase
	9	DB Treatment End Point 	<=1	1	DB Treatment
	10	Withdrawal Baseline	2 to 20	14	Withdrawal
	11	Withdrawal Week 2 Follow Up 	> DB or >Withdrawal	7 to 21	Withdrawal Follow Up

CCI

 Relative to Study Day 1 in each of the Lead-in, the double-blind treatment and the withdrawal period

 End Point is defined as the last non-missing post-baseline measurement during the double-blind treatment period.

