#### 4.3.2. Analysis Methods

The secondary efficacy endpoints will be analyzed for both the eITT and fITT analysis sets.

For all continuous secondary efficacy endpoints, descriptive statistics of actual values and mean changes from baseline at each scheduled time point will be provided by treatment group for the lead-in period, the double-blind treatment period and the withdrawal period. A mean-SE plot over time will be presented for observed values during the lead-in period, the double-blind treatment period and the withdrawal period by treatment group.

For each of the continuous secondary efficacy endpoints, the JNJ-42165279 treatment group will be compared to placebo using the same MMRM model as for the HDRS17 total score.

To explore the results for the subgroup of placebo responders, descriptive statistics of actual values and mean changes from baseline for the continuous secondary endpoints at each scheduled time point will be provided by treatment group for the lead-in period, the double-blind treatment period and the withdrawal period for the fITT subset of placebo responders. Mean-SE plots over time will also be presented for this subgroup.

Frequency tables and figures for the categorical secondary efficacy endpoints will be provided at each scheduled time point by treatment group for the lead-in period, the double-blind treatment period and the withdrawal period. Chi square test will be used to test the overall differences between the treatment groups at week 6 of the double-blind treatment period. If deemed appropriate, Cochran–Mantel–Haenszel test with (pooled) center as stratification factor will be performed.

A cumulative distribution plot of the percent reduction in HDRS17 total score from double-blind treatment baseline at Week 6 of the double-blind treatment period will be provided. A similar plot will be provided for the SIGH-A total score percent reduction.

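### CGI-I response at Week 6 includes placebo lead-in improvement, because the scale is anchored at admission and the responder test does not use the Visit 5 rating; this costs sensitivity, not validity

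*SAP*

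**What the plan says.** **Anchor.** The rating form in Protocol Attachment 2 asks: "Compared to his/her condition at admission to the project, how much has the patient changed". SAP 4.3.1, like Protocol 3.2, describes the scale as change "relative to a baseline state at the beginning of the intervention" and does not say which period is meant.

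**Lead-in and blinding.** SAP 1.2: "The first period is a placebo lead-in of 3 weeks for all subjects". Protocol 3.1: "Investigators and subjects will be blinded to exact duration of each subject-specific lead-in period throughout the study". The Time and Events Schedule has the first CGI-I at Visit 3, within the lead-in, and further ratings at every visit to Visit 10.

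**Responder definition and test.** SAP 4.3.1: "Responders on the CGI-I are defined as subjects with a score of 1 very much improved or 2 much improved". For categorical secondary endpoints, SAP 4.3.2 says: "Chi square test will be used to test the overall differences between the treatment groups at week 6 of the double-blind treatment period". A Cochran–Mantel–Haenszel test by pooled center may be added. Neither test has a baseline term.

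**Visit 5.** SAP Table 1 (section 2.5) gives CGI-I a Visit 5 row labelled "DB Treatment Baseline". The HDRS17 and SIGH-A response endpoints in 4.3.1 are percentage changes from that same baseline. The CGI-I responder definition does not refer to it.

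**The concern.** A Week 6 CGI-I covers about nine weeks from admission: three on placebo before randomisation and six on randomised treatment. Because raters are blinded to the end of the lead-in, they cannot move the reference point to the start of the treatment period. A subject who was much improved by Visit 5 and stays so is counted as a Week 6 responder in whichever arm he or she joins, whatever the drug does.

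Two things are at stake. The responder percentages in each arm cannot be read as response to six weeks of treatment, and the test loses sensitivity. The effect should be smaller in eITT, which excludes subjects with at least 40% HDRS17 improvement in the lead-in. It should be larger in fITT, which keeps them and where the chi-square or CMH test is not stratified by lead-in response status.

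**Working it through.** **Figures in the plan.** The documents give no CGI-I rate, power or sample size. The only stated size is for HDRS17 (SAP 1.4): effect size 0.45, one-sided alpha 0.20, power 90%. It reproduces: n = 2 × (0.8416 + 1.2816)² / 0.45² = 2 × 4.508 / 0.2025 = 44.5, so 45 per arm. That 45 is used below as the eITT size per arm. All CGI-I inputs are assumptions.

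**1. Dilution of the responder difference.** Let q be the share rated 1 or 2 at Visit 5, r the share of those still rated 1 or 2 at Week 6, and p the Week 6 response rate among the rest.

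- Rate in an arm = q·r + (1 − q)·p
- Difference = (1 − q)(p_drug − p_placebo) + q(r_drug − r_placebo)

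If r is equal in both arms, the second term vanishes and the difference shrinks by the factor (1 − q). With p = 45% and 30%, and r = 80% in both arms:

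| q | Drug | Placebo | Difference |
|---|---|---|---|
| 0 | 45.0% | 30.0% | 15.0 points |
| 5% | 0.0400 + 0.4275 = 46.75% | 0.0400 + 0.2850 = 32.5% | 14.25 |
| 10% | 0.080 + 0.405 = 48.5% | 0.080 + 0.270 = 35.0% | 13.5 |
| 20% | 0.16 + 0.36 = 52.0% | 0.16 + 0.24 = 40.0% | 12.0 |
| 25% | 0.2000 + 0.3375 = 53.75% | 0.2000 + 0.2250 = 42.5% | 11.25 |

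At q = 10%, 0.08/0.35 = 23% of placebo responders and 0.08/0.485 = 16% of drug responders were already responders at Visit 5. At q = 25% the shares are 0.20/0.425 = 47% and 0.20/0.5375 = 37%. The planning assumption of 25% lead-in response (SAP 1.4) concerns HDRS17, but it makes the last row a plausible guide to fITT. The 5 to 10% rows are closer to eITT.

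**2. Precision forgone.** A latent-normal simulation used 45 per arm, an effect of 0.35 SD, one-sided 0.20 (borrowed from the primary analysis), assumed cut-points, a linear model for the score and 4,000 trials per setting. The Monte Carlo standard error is about √(0.8 × 0.2/4000) = 0.6 points.

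| Analysis at Week 6 | Power | Variance relative to unadjusted score |
|---|---|---|
| Responder chi-square | 70–71% | – |
| 7-point score, unadjusted | 77–79% | 1 |
| Adjusted for Visit 5, correlation 0.3 | 79% | 0.94 |
| Adjusted for Visit 5, correlation 0.5 | 83% | 0.80 |
| Adjusted for Visit 5, correlation 0.6 | 86% | 0.71 |

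The last three rows agree with direct arithmetic. Power of 78% at one-sided 0.20 implies a standardised effect of 0.772 + 0.842 = 1.614. Dividing by √0.94, √0.80 and √0.71 gives 1.665, 1.804 and 1.915. Subtracting 0.842 leaves 0.823, 0.963 and 1.074, that is, power of 79%, 83% and 86%.

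About 7 to 8 points of the gap from the chi-square therefore come from keeping seven categories, and about 1, 5 and 8 points from the Visit 5 adjustment.

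**The case against.** **Validity.** The carry-over arises before randomisation, which is 1:1 and stratified by lead-in response status, so it is equal between arms in expectation. This stands in full. A reader might infer that the CGI-I result is biased, or that it does not answer whether six weeks of drug changed global status. The documents do not support that. The randomised Week 6 difference in improvement since admission is an effect of the six weeks; it is only a less sensitive measure of it.

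**Is Visit 5 really unused?** SAP 4.3.2 provides frequency tables for categorical secondary endpoints at each scheduled time point, lead-in included, by arm. The Visit 5 responder rate would therefore be visible; it is the test that leaves it out. The SAP also does not say whether the 7-point score is treated as continuous. If it is, the common MMRM would bring in the Visit 5 value as double-blind baseline. The point is exact only for the responder chi-square or CMH.

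**Do the anchors conflict?** Not necessarily. The beginning of the intervention can mean Day 1, when blinded study medication starts, which agrees with the form. The wording is ambiguous, not contradictory.

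**Size.** Every CGI-I rate above is assumed. If the drug helps early responders keep their rating, the second term of the formula offsets some of the dilution. In the first 14 subjects (SAP section 2), the two singled out for substantial improvement (40% and 41%) both meet the 40% definition and so fall outside eITT. A small q in eITT is plausible, though subjects just under 40% could still be rated much improved.

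**Attribution.** The whole gap from about 70% to 79–86% power must not be charged to the anchor, since about half or more of it comes from dichotomising.

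**Conclusion.** The point holds as a loss of interpretability and sensitivity on a supportive endpoint. Week 6 CGI-I response counts lead-in improvement in both arms, and the responder test does not use a pre-treatment rating that is already collected. There is no bias between arms and no inflation of type I error.

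On the assumed rates, with early responses kept equally in both arms, the loss is 0.75 to 1.5 points out of 15 at q = 5 to 10% and 3.75 points at q = 25%. Adjusting the 7-point score for Visit 5 would lower the treatment-effect variance by about 6 to 30% at correlations of 0.3 to 0.6, worth about 1 to 8 power points over the unadjusted score.

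The stakes are limited. CGI-I is secondary in SAP Table 2 but exploratory in Protocol 9.3.2, SAP 4.1.1 controls error only for the primary analysis, and the HDRS17 primary analysis is untouched.

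**What to change.** - **SAP 4.3.1:** state that CGI-I is anchored at admission, before the lead-in.
- **SAP 4.3.2:** compare the Week 6 7-point CGI-I score between arms, adjusting for the Visit 5 CGI-I score and country, for example with a proportional-odds model. If the common MMRM was meant to cover the CGI-I score, say so, since it would already carry the Visit 5 adjustment.
- **Responder table:** keep it descriptive, with the Visit 5 responder rate by arm beside the Week 6 rate.
- **Optional:** report new Week 6 responders among subjects not rated 1 or 2 at Visit 5. This is for interpretation, not power: in the same simulation the restriction gave 66–67%, against 70–71% for the unrestricted chi-square.

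The cost is SAP wording and one model. Visit 5 CGI-I is already scheduled, so no new data and no change at sites are needed.
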